6.1.2 Background and demographic characteristics

Baseline demographic and background data will be summarized by treatment group using contingency tables for the qualitative variables (sex, race, age group and body mass index group; established cardiovascular disease at baseline yes/no) and the mean, standard

deviation, median, minimum and maximum for the quantitative variables (age, height, body mass index, waist circumference). Body mass index (BMI) will be calculated from the collected variables height and weight. ($BMI = \text{weight} / \text{height}^2$, where weight is in kg and height is in m.)

Summaries and listings will use the ITT population.

Baseline comparability among the four treatment groups for demographic variables (as described above) and baseline efficacy variables (HbA_{1c}, FPG, 2-hr post-OGTT glucose value) will be examined using the Cochran-Mantel-Haenszel test for qualitative variables and an F-test for quantitative variables. These p-values are provided for descriptive purposes, and are not to be considered to define any formal basis for determining factors which should be included in statistical analysis models.

6.1.3 Study medication

Duration in the trial, as well as duration on study treatment (i.e. excluding interruptions) will be summarized by drug (or matching placebo) for the four treatment groups. The number of patients on each dose level of nateglinide and valsartan (and number of patients who have discontinued study medication) will be presented at each visit.

6.1.4 Concomitant therapy

Prior medications and significant non-drug therapies (as coded using the WHO dictionary) will be summarized by treatment group. Listings will be presented by treatment group and patient number.

The specified concomitant medications (see section 3.4.7 of this protocol) will be summarized and listed overall by preferred term and treatment group, and at each visit by type of medication and treatment group.

Summary statistics will be presented by treatment group and visit for the evaluation of lifestyle conduct (see Section 3.5.5).

6.1.5 Efficacy evaluation

6.1.5.1 Primary efficacy analysis

There will be three primary variables in the study:

- Time to progression to diabetes (on a discrete time scale)
- Time to first extended cardiovascular endpoint after randomization (in days since randomization)
- Time to first core cardiovascular endpoint after randomization (in days since randomization)

These variables will be analyzed using a closed testing procedure for each drug. The three endpoints will be tested in a parallel manner for each drug (Table 6). There will be unequal weights for tests of the progression to diabetes and the cardiovascular endpoints.

Due to the discrete nature in which time to diagnosis of diabetes is measured (every six months for fasting glucose from visits 6-11, every twelve months for post-prandial glucose), a score test will be used based on a discrete time proportional odds model (Cox's [16] model for discrete time data, discussed also in [17]) for the effect of nateglinide (valsartan) stratified for valsartan (nateglinide) and history of cardiovascular disease at baseline (yes/no – see section 3.3.2 for a definition). This model is analogous to TIES = DISCRETE in the SAS® procedure PHREG.

For the first three years in study the time intervals used in the model will be defined by the six-monthly study visit period of the visit at which it was detected (in line with the definition of progression to diabetes (Section 3.5.3), a confirmatory measurement has to take place at a repeat visit). If progression was detected at an unscheduled visit (or defined by the diabetes adjudication process), it will be assigned to the next regular six-monthly visit. After three years FPG/OGTT assessment intervals are yearly.

For the endpoints 'time to first extended/core cardiovascular event', the effect of nateglinide (valsartan) will be tested using a logrank statistic, stratified for valsartan (nateglinide) and for history of cardiovascular disease at baseline (yes/no). That is, a score test will be implemented, with TIES = EXACT in the SAS® procedure PHREG. If not otherwise stated, all efficacy analyses will be performed on the ITT population.

Progression to diabetes and cardiovascular endpoints are defined as in Section 3.5.3 of the protocol.

The six null hypotheses will be:

- N1 There is no difference between the nateglinide and non-nateglinide treated groups in time to progression to diabetes.
- N2 There is no difference between the nateglinide and non-nateglinide treated groups in time to first extended cardiovascular endpoint.
- N3 There is no difference between the nateglinide and non-nateglinide treated groups in time to first core cardiovascular endpoint.
- V1 There is no difference between the valsartan and non-valsartan treated groups in time to progression to diabetes.
- V2 There is no difference between the valsartan and non-valsartan treated groups in time to first extended cardiovascular endpoint.
- V3 There is no difference between the valsartan and non-valsartan treated groups in time to first core cardiovascular endpoint.

Testing will be done using the closed testing procedure described in Section 6.1, Table 6, using a 2.5% one-sided alpha level. Nateglinide or valsartan will be declared superior to non-nateglinide/non-valsartan for a primary endpoint if the respective intersection hypotheses (see Table 6) can be rejected in favor of the experimental drug using the adjustment criteria as specified in Section 6.1.7 "Interim analyses".

The interaction effect of nateglinide and valsartan will be tested in separate models that include an interaction term. For the progression to diabetes, this will be done by a discrete time proportional odds model. For the cardiovascular endpoints, a standard Cox models (on a continuous time scale) will be applied, using a TIES=EXACT option in SAS. In each of these

models, the two treatment effects, and history of cardiovascular disease at baseline will be fitted as covariates, in addition to the interaction term.

Two-sided 95% confidence intervals of the hazard ratio will be presented for each of the primary comparisons.

This factorial trial is testing two drugs, and therefore can be considered a combination of two trials into one. The combined type I error probability of two independent trials (one for each drug, each using 5% alpha-level) is 9.75%. As the overall type I error of this trial will be exactly the same, a 5% alpha-level will be used for each of the two experimental treatments.

The primary analysis will be on the ITT population, but the models will also be performed as supportive analysis for the per-protocol population.

Confidence intervals will be calculated for the hazard ratio in two-group treatment comparisons of the two monotherapies vs. placebo, combination therapy vs. placebo, and combination therapy vs. the two monotherapies.

Another sensitivity analysis will be performed for the ITT population, in which time after the permanent discontinuation of study treatment will be considered as censored.

The impact of baseline and demographic characteristics on the primary outcomes will be explored. The factors to be explored (individually or in the same model) will include:

- Country
- Fasting plasma glucose at baseline
- 2-hr prandial glucose at baseline
- Age at baseline
- Sex
- Race
- Body mass index at baseline
- Waist circumference at baseline

The methodology used for these explorations will be the same as that used for exploration of the interaction of nateglinide and valsartan, with the factor(s) to be explored in the model instead of the interaction term.

Subgroup analyses will be performed for patients with and without established CHD at baseline, male and female patients, by race, age group, low and high body mass index, low/high fasting glucose at baseline, and low/high post-prandial glucose at baseline, patients taking ACE-inhibitors at baseline, and patients with hypertension at baseline.

Supportive analyses will be presented on the glucose results at the end of the withdrawal period: Change from baseline (week 0) in fasting glucose and in post-prandial (2hr) glucose will be tested for each drug by means of a general linear model. Center, baseline value, history of CVD at baseline (yes/no), and the two experimental treatment effects will be the variables in the model. Summary statistics will be presented by treatment group for the glucose values at baseline and at the end of treatment.

The final analysis is foreseen to be performed (event-driven, not time-driven) when 1374 patients have experienced an Adjudication Committee-confirmed extended CV endpoint.

Kaplan-Meier plots of the event rates by treatment group will be presented for each primary endpoint.

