3.3.2 Inclusion and exclusion criteria

Inclusion criteria

- Written informed consent to participate in this study.
- Males and females. Females must be surgically sterile or postmenopausal.
- Age 50 years or older
- Presence of RF(s) (see Table 1) or CVD(s) (see Table 2) at Visit 1
 - age 50 to 54 years - 1 or more CVD(s)
 - age 55 years and older - 1 or more RF(s) or 1 or more CVD(s)
- FPG ≥ 95 mg/dL (5.3 mmol/L) and less than 126 mg/dL (7.0 mmol/L) at Visit 1
- 2hr post-challenge glucose (after a 75-g OGTT) ≥ 140 mg/dL (7.8 mmol/L) but less than 200 mg/dL (11.1 mmol/L) at Visit 1
- Ability and willingness to comply with all study requirements

Table 1 Cardiovascular risk factors (RFs)

• Family history of premature CHD (definite myocardial infarction or sudden death before 55 years of age in father or other male first-degree relative, or before 65 years of age in mother or other female first-degree relative)• Current cigarette smoking (defined as smoking at least 10 cigarettes/day on a regular basis for at least 5 years prior to inclusion in the study; if the patient has quit smoking, s/he will be considered a smoker if she/he stopped less than 12 months before inclusion)• Hypertension (>140mm Hg systolic or 90mm Hg diastolic or on anti-hypertensive medication)• Low HDL cholesterol (<40 mg/dL [1.0 mmol/L])• High LDL (\geq 160 mg/dL [4.1 mmol/L]) or high non-HDL (\geq190 mg/dL [4.9 mmol/L]) if triglycerides are >200 mg/dL (2.3 mmol/L) or on lipid-lowering therapy.• Left ventricular hypertrophy with strain pattern defined as per ECG (Sokolow and Lyon criteria or Cornell criteria)• Known microalbuminuria (>30 mg/g creatinine)

Table 2 Cardiovascular Diseases (CVD)

• Previous myocardial infarction (>1 month ago)• Stable angina or unstable angina (>1 month ago) each with documented multivessel coronary disease; >50% stenosis in at least two major coronary arteries, or positive stress test• Multivessel PTCA >1 month ago• Multivessel CABG > 4 years ago or with angina• Previous limb bypass surgery or percutaneous angioplasty• Previous non-traumatic limb or foot amputation• History of intermittent claudication with ankle:arm blood pressure ratio of \leq 0.80 in at least one side• Significant peripheral stenosis (>50%) documented by angiography• Stroke of atherosclerotic origin >1 month ago

Exclusion criteria

- Failure to provide written informed consent

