3.5.3 Efficacy assessment

Efficacy assessments will be performed at every visit following randomization.

Primary endpoint: time to progression to diabetes (V1, N1)

In order to assess patients' diabetic condition the following procedure must be followed: When a patient has an FPG \geq 126 mg/dL (7.0 mmol/L) or a 2hr post-challenge glucose \geq 200 mg/dL (11.1 mmol/L) during the trial, a repeat OGTT should be performed as soon as possible (on a different day), preferably within 4 weeks (28 days) but not later than 12 weeks (84 days) after the day of the initial laboratory assessment indicative of diabetes. If, for whatever reason, a repeat OGTT cannot be performed, at least an FPG should be performed at that time.

The progression to diabetes endpoint is defined through (a) an algorithm based on central laboratory measurements of FPG and/or 2hr OGTT, or (b) adjudication by the Diabetes Endpoint Adjudication Committee as follows:

1. Endpoint definition based on laboratory tests: FPG \geq 126 mg/dL (7.0 mmol/L) or a 2hr post-challenge glucose (OGTT) \geq 200 mg/dL (11.1 mmol/L) during two consecutive valid measurements that are within 12 weeks (\leq 84 days) but at least one day apart. The time to progression to diabetes is defined as the time of the original measurement (subsequently confirmed) of an FPG \geq 126 mg/dL (7.0 mmol/L) or a 2hr post-challenge glucose \geq 200 mg/dL (11.1 mmol/L).
2. Adjudication by the Diabetes Endpoint Adjudication Committee: progression to diabetes may be confirmed by the Committee in cases suggestive of diabetes but where above laboratory test-based definition does not hold (e.g. due to missing central laboratory measurements or repeat tests outside the 12-week time limit). E.g., the Committee will adjudicate cases where diabetes has been diagnosed by a primary care physician (possibly based on local laboratory assessments) and/or where anti-diabetic medication has been initiated; adjudication also includes deciding on the time to progression to diabetes. Details of adjudication are provided in a Diabetes Endpoint Adjudication Charter to be followed by the Committee.

An HbA_{1c} measurement cannot replace an FPG or a 2hr post-challenge glucose to confirm progression to diabetes.

Primary endpoint: extended CV endpoint (V2, N2)

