3.5.5 Other assessments

Screening visit (Visit 1) information

The following information will be collected at Visit 1: demographics, vital signs, waist circumference, concomitant medication, medical history. In addition, laboratory measurements will be performed. All information except medical history, concomitant

medication, and laboratory measurements will be collected using IVRS. Also, the decision to randomize or discontinue the subject from screening, including the reason for discontinuation, will be recorded using IVRS. All Visit 1 screening information will be transferred from IVRS to the trial database.

2hr OGTT (with FPG, post-prandial glucose)

Subjects have to be fasting at each OGTT assessment. A fasting and 2hr post-challenge glucose evaluation is required at Visit 1 to confirm eligibility of screened subjects. Post-randomization OGTT will be performed at Visit 7 (Month 12), annually thereafter, and at the final visit (for exceptions see below). Repeat OGTT to confirm a glycemic endpoint will be performed as soon as possible (on a different day), preferably within 4 weeks (≤ 28 days) but no later than 12 weeks (≤ 84 days) following the day of the initial laboratory assessment that indicates diabetes. If, for whatever reason, a repeat OGTT cannot be performed, at least an FPG should be performed at that time.

For patients who have progressed to diabetes and have had an FPG ≥ 300 mg/dL (16.7 mmol/L), an annual OGTT is no longer required; an FPG, however, should still be performed. An annual OGTT is still required for all patients with FPG < 300 mg/dL.

In patients who have progressed to diabetes HbA_{1c} will be measured at time point 0 minutes of positive, confirmatory OGTT and annually thereafter.

Patients who achieved a confirmed glycemic endpoint must withhold the morning dose of any antidiabetic treatment, in addition to the study medication, prior to each subsequent OGTT assessment.

The OGTT must initiate (0 minute sample) no later than 10:00 a.m.

Subjects are given a 75 gram glucose-equivalent oral glucose challenge. The glucose solution is centrally provided to all centers. A venous sample will be taken 2 hours post-challenge to evaluate glucose levels (see table below).

Table 5 OGTT assessment

	Time (minutes) Post Glucose Administration	
	0+	120
75 g glucose	X	
Plasma glucose	X	X
HbA _{1c} ++	X	

Life-style intervention education

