6.2 Sample size and power considerations

The original sample size calculation is based on an event rate of 4% (i.e. 4% of the population experiencing at least one event) per year for the extended cardiovascular endpoints in the placebo group. This assumption is based on risk score calculation for baseline characteristics of early patients recruited into NAVIGATOR. A reduction in the annual hazard rate of 20% under treatment is considered clinically significant. An accrual time of 18 months, and further four-year, three month follow-up was used for the sample size calculation. This will give a total trial duration of five years and nine months from first patient first visit (which can vary if event rates are not as expected, as the timing of the final analyses will be driven by the number of patients with events). The reductions in hazard (under treatment) as compared to patients receiving placebo was assumed to be 20% for both nateglinide and valsartan monotherapy.

For the combination group, the effect size in comparison to placebo is 36%, assuming the effects of the two drugs are independent. Although there is no known drug-drug interaction between valsartan and nateglinide, an effect size of this magnitude is ambitious. The sample size calculation was therefore based on a "subadditivity / 75% additivity of effects" approach, assuming an effect size of 32% on cardiovascular outcome of the two drugs in combination. The treatment discontinuation rate was assumed to be 30% over five years, corresponding to approximately 6.9% per annum. While patients on treatment were assumed to have the full effect (i.e. 20% reduction of hazard rate if in the monotherapy group), it was assumed that patients who discontinued treatment would have only $\frac{1}{4}$ of the treatment effect remaining as

carry-over effect. Furthermore, it was expected that 75% of the patients who discontinued treatment could be followed up for events. The remaining 25% would comprise patients completely lost to follow-up, patients who die (without reaching a primary endpoint), and those for whom events are unintentionally not reported by the investigator.

Based on these assumptions, a total of 9152 patients will provide 90% testwise power to detect a treatment difference in the extended cardiovascular endpoint.

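### The primary diabetes test is valid but leaves out baseline fasting and 2-hour glucose, and so gives up some efficiency; the size depends on a prognostic strength the protocol does not state

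*Protocol*

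**What the plan says.** Section 6.1.5.1 states that for progression to diabetes "a score test will be used based on a discrete time proportional odds model", for the effect of each drug "stratified for valsartan (nateglinide) and history of cardiovascular disease at baseline". No glucose term enters that test.

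Both glucose values exist for every eligible patient. Section 3.3.2 requires "FPG ≥ 95 mg/dL (5.3 mmol/L) and less than 126 mg/dL (7.0 mmol/L) at Visit 1" and "2hr post-challenge glucose (after a 75-g OGTT) ≥ 140 mg/dL (7.8 mmol/L) but less than 200 mg/dL (11.1 mmol/L) at Visit 1". Section 3.5.5 adds: "A fasting and 2hr post-challenge glucose evaluation is required at Visit 1 to confirm eligibility of screened subjects". Section 3.3.1 allows no deviation from the entry criteria.

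The endpoint rests on the same two measurements. Section 3.5.3 says "The progression to diabetes endpoint is defined through (a) an algorithm based on central laboratory measurements of FPG and/or 2hr OGTT", with committee adjudication as the second route.

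Later in 6.1.5.1, "The impact of baseline and demographic characteristics on the primary outcomes will be explored", and the list of factors includes baseline fasting and 2-hour glucose. Low and high values of each also define subgroups. In the linear models for change in glucose (6.1.5.1 and 6.1.5.2), by contrast, the baseline value is a covariate.

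**The concern.** In a logistic or proportional-hazards type model, leaving out a strong predictor of outcome moves the estimated treatment coefficient toward zero and lowers the expected test statistic. Starting glucose is a natural candidate for such a predictor when the event is a glucose value crossing a fixed cut-off.

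What is at stake is the diabetes claim if the true effect is smaller than planned. Section 3.2 gives diabetes one-sided 0.5% of the alpha, and Table 6 relaxes this only under demanding conditions, set out below. The stated diabetes power above 99% (section 6.2) rests on an assumed 25% hazard reduction per drug and 6% yearly progression. Section 6.1.7 records that the cardiovascular event rate has already fallen short of expectation.

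**Working it through.** **1. Reproducing the plan's figures.** The inputs are all from section 6.2: 9152 patients in four equal arms; accrual of 18 months plus 4 years 3 months of follow-up; 30% discontinuation over five years, with a quarter of the effect retained and 75% of discontinued patients followed. Cardiovascular: 4% per year, 20% reduction per drug, 32% combined. Diabetes: 6% per year, 25% per drug, 39.1% combined. A four-arm cohort model gives:

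- Extended cardiovascular endpoint: 1378 events (stated 1374), power 89.4% (stated 90%).
- Diabetes: about 1917 events, and an effective pooled hazard ratio of 0.8013, in line with the 20% reduction in Table 7.

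Power = Φ(√(D·g/4)·|ln HR| − z), where D is the number of events and g the information multiplier. With D = 1917, g = 1 and HR = 0.8013, √479.25 × 0.2215 = 4.849.

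- At one-sided 0.02495 (section 6.1.7): Φ(4.849 − 1.961) = 99.8%, which reproduces the stated figure of above 99%.
- At the diabetes share, 0.2 × 0.02495 = 0.00499: Φ(4.849 − 2.577) = 98.9%.

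**2. When the 0.005 level binds (Table 6, nominal levels).** Suppose the diabetes p-value lies between .005 and .025.

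- Its intersection with the extended endpoint can then be rejected only if the extended p-value is below .025. The same holds for the core endpoint.
- The three-way hypothesis must be rejected through the cardiovascular tests: one p-value below .01 (with the mild trimming condition on the other), or both below .02.
- When all this holds, the core endpoint is itself significant. Table 7 gives that 67.1% power, so under Table 7's assumptions the easier route is closed in at least 100 − 67.1 = 32.9% of trials.

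**3. Information gained by adjustment.** The gain is the squared ratio of adjusted to unadjusted treatment z, from large simulated discrete-time logistic models with yearly intervals (an approximation to the planned model, without discontinuation). Example, eight years, HR 0.80, hazard ratio 2.0 per SD: the coefficient goes from −0.2117 to −0.2345 and the standard error rises by a factor of 1.013, so (0.2345/0.2117/1.013)² ≈ 1.195, a gain of about 19.5%.

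| Assumed HR per SD of glucose score | 5 years | 8 years |
|---|---|---|
| 1.3 | 2% | 3% |
| 1.5 | 4% | 6% |
| 1.7 | 7% | 11% |
| 2.0 | 13% | 20% |
| 2.5 | 24% | 35% |

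A separate check gave 1-2% at 1.3 and 28-34% at 2.7. A threshold model with the protocol's entry windows, the 126 and 200 mg/dL cut-offs and the confirmation rule, under six sets of assumed measurement noise and drift, gave 9.1, 9.7, 12.8, 13.4, 16.4 and 18.1%.

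**4. What it does to power.**

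- *Planned effect (HR 0.8013, 1917 events):* with g = 1.05 to 1.30, 98.9% becomes 99.2-99.8% at the diabetes share.
- *HR 0.88, 1917 events:* Φ(2.798 − 2.577) = 59% becomes 61-73%.
- *15% reduction, one-sided 0.005, eight years (simulation):* about 92% to 95% when the SD of the log-hazard contribution is 0.5 (e^0.5 = 1.65 per SD), and about 78-81% to 91-94% when it is 1.0 (e^1.0 = 2.72).

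The eight-year figures agree roughly with step 3. A power of 92% means z = 2.576 + 1.405 = 3.981; multiplied by √1.11 this is 4.194, and Φ(4.194 − 2.576) = 94.7%. A power of 81% means z = 3.454; multiplied by √1.34 this is 3.998, giving 92.2%.

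**The case against.** The strongest reply is that nothing here is an error. A pre-specified stratified score test controls type I error, and an effect not conditioned on glucose is a legitimate target. This stands: a reader might infer that the primary test is biased or invalid, and the documents do not support that. Movement of the coefficient toward zero is a property of odds and hazard ratios, not a flaw in the test. A valid test can still be inefficient, however.

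Second, the trial has ample diabetes power. Section 6.2 says above 99% and Table 7 above 99.9%. This also stands under the plan's own effect, so it would be wrong to infer that the trial is underpowered for diabetes. The 15% scenario is the reviewer's choice; the plan's comparable pooled figure is the 20% in Table 7. Sections 3.1 and 3.2 now project about eight years, which raises unadjusted power further, and the eight-year figures above allow for that.

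Third, glucose-adjusted models are already planned. They are, but as explorations, and an exploratory model cannot carry the primary claim.

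Fourth, an efficacy interim took place in December 2005, so a change of primary test needs justification to regulators. That is a real cost. But the Executive/Steering Committee is blinded (3.1.1.1), as are the personnel monitoring the trial until database lock (3.2), so a decision made without knowledge of results remains possible.

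A reader might also infer that history of cardiovascular disease was made a stratum only for the sake of the cardiovascular endpoints. The protocol does not say so, and section 3.1 mentions cardiovascular disease status among the information received before assignment.

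**Conclusion.** The point holds as a cheap improvement, not as a defect that endangers the trial. The primary diabetes test omits two baseline values that every patient has and that are measured by the same tests as the endpoint.

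No single percentage can be read off the documents, because prognostic strength is not given. The range runs from 1-3% at a hazard ratio of 1.3 per SD to 24-35% at 2.5-2.7. The threshold model's 9-18% is tied most closely to this trial's entry windows, but it too rests on assumed noise and drift. Under the planned effect the benefit is negligible; it is protection against a smaller true effect.

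The eight-year power levels depend on assumed loss to follow-up and on limited simulation, so the direction and rough size of the gain are firmer than the levels. They also hold the glucose-conditional effect fixed at 15%, which is why unadjusted power falls as prognostic strength rises.

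**What to change.** By amendment before unblinding, decided by people with no access to the interim results, change section 6.1.5.1 as follows:

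- Add Visit 1 fasting glucose and Visit 1 2-hour glucose as continuous covariates, with their functional form fixed in advance, to the stratified discrete-time model that gives the primary diabetes test and estimate.
- Label the resulting effect as conditional on baseline glucose.
- Keep the present stratified score test as a supportive analysis.
- Leave the cardiovascular logrank tests unchanged.

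No new data are needed, and section 6.1.5.1 already plans the same class of model with these covariates. The costs are an effect measure conditional on baseline glucose and a short justification for changing a primary test after an efficacy interim.

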3.1 Overall study design

[figure not shown]
This is a multinational, randomized, double-blind, placebo-controlled, forced-titration, 2 x 2 factorial design trial to assess the effect of nateglinide and valsartan on the prevention of diabetes and cardiovascular events in subjects with impaired glucose tolerance (2hr post-challenge glucose > 140 mg/dL/7.8 mmol/L but < 200 mg/dL/11.1 mmol/L and FPG ≥ 95 mg/dL/5.2 mmol/L but < 126 mg/dL/7.0 mmol/L) and increased risk for a cardiovascular event. The three primary efficacy endpoints of this study are time to progression to diabetes, time to first occurrence of an extended CV endpoint and time to first occurrence of a core CV endpoint. These three endpoints will be tested in parallel using a closed testing procedure for each drug. It is thus possible to achieve statistical significance for any one endpoint independent of the others.

Originally, two formal efficacy interim analyses were foreseen which were to take place when approximately 687 and 1031 subjects had had an extended CV endpoint, corresponding to 50% and 75% of the 1374 target subjects, respectively (Section 6.1.7 of the study protocol). A first formal interim analysis was performed in December 2005 with 412 patients (30% of the target subjects) having experienced an extended CV endpoint. The second efficacy interim analysis will not be conducted.

Approximately 9152 subjects from 800-900 centers in approximately 39 countries are to be randomized. Screening for eligibility will take place 1 month prior to treatment start and requires an oral glucose tolerance test (OGTT) to confirm eligibility. After receipt of the appropriate baseline data and cardiovascular disease status, eligible subjects will be randomly assigned to one of the four treatment groups (ratio 1:1:1:1), i.e. nateglinide 60 mg ac, valsartan 160 mg od, the combination of nateglinide 60 mg ac and valsartan 160 mg od, or placebo, using a computerized interactive voice response system (IVRS).

Study accrual is expected to require approximately 18 months. A total of 1374 patients with an extended CV endpoint are required. A total duration of follow-up of 5 years and 9 months after FPFV is anticipated under the original protocol assumptions. Based on the observed CV event rate at the time of Amendment No. 5, the projected total duration of the trial is approximately 8 years.

A diagram of the study design is shown below with times indicated relative to treatment start:

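### The four primary CV tests adjust only for the other drug and CVD history; adding age, sex and lipids would recover a modest amount of power (about 1 to 2 points on the extended endpoint, under an assumed prognostic strength)

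*Protocol*

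**What the plan says.** - **Test.** Section 6.1.5.1 says that for both CV endpoints the effect of each drug "will be tested using a logrank statistic, stratified for valsartan (nateglinide) and for history of cardiovascular disease at baseline (yes/no"), run as a score test in PHREG. Section 6.1 names the same two stratification factors.
- **Use of the result.** The p-values enter the closed procedure: "Testing will be done using the closed testing procedure described in Section 6.1, Table 6, using a 2.5% one-sided alpha level". Section 6.1.7 lowers the final level to 0.02495.
- **Other baseline factors.** Section 6.1.5.1 adds "The impact of baseline and demographic characteristics on the primary outcomes will be explored". Its list has country, fasting and 2-hour glucose, age, sex, race, BMI and waist. Lipids and smoking are not on it. These models are exploratory and do not feed Table 6.
- **Data at hand.** Section 3.5.5 collects demographics, vital signs and medical history at Visit 1. Section 3.5.4 measures total cholesterol, triglycerides, LDL and HDL at Visit 1. In section 3.3.2 the entry rule depends on age ("age 55 years and older - 1 or more RF(s) or 1 or more CVD(s")), and Table 1 there lists smoking and lipids as risk factors.
- **Sizing.** Section 3.1: "A total of 1374 patients with an extended CV endpoint are required". Section 6.2: "a total of 9152 patients will provide 90% testwise power to detect a treatment difference in the extended cardiovascular endpoint". The placebo assumption is "an event rate of 4% (i.e. 4% of the population experiencing at least one event) per year", and on its source section 6.2 says "This assumption is based on risk score calculation for baseline characteristics of early patients recruited into NAVIGATOR".

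**The concern.** The protocol treats age, lipids and other baseline characteristics as predictors of CV risk when it selects patients, and uses baseline risk when it sets the event rate. It then leaves all of them except CVD history out of the confirmatory CV tests.

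In a time-to-event analysis, unexplained differences in risk within a stratum pull the estimated hazard ratio towards 1, and the test loses some power. The type I error is not affected.

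The CV tests are the ones with little power to spare. They set the 9152 patients and the 1374 events, whereas section 6.2 gives the diabetes endpoint more than 99% testwise power. The point is therefore confined to N2, N3, V2 and V3.

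**Working it through.** **1. Reproduce the stated design (inputs from section 6.2).**
- Placebo hazard: −ln(0.96) = 0.0408 per year.
- Hazard reductions by arm: 0, 20%, 20% and 32%.
- Discontinuation 6.9% per year, with a quarter of the effect kept afterwards and 25% of those who discontinue not followed for events.
- Follow-up spread uniformly over 4.25 to 5.75 years.

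Expected events per arm are about 406, 338, 338 and 296, about 1380 in all before rounding (stated: 1374). The pooled hazard ratio (HR) is 0.840.

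Power = Φ(√D × |ln HR| / 2 − 1.96). With D = 1380 and HR 0.8398 this is Φ(37.15 × 0.0873 − 1.96) = Φ(1.28) = 90.0%, as stated. Solving for 1374 events and 90% power gives HR 0.8395, which matches the 16% reduction in Table 7. The stated figures therefore hold without covariate adjustment.

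**2. Loss from leaving out a prognostic covariate.** Let the omitted covariate multiply the hazard by U, lognormal with mean 1 and log-hazard SD σ. At cumulative hazard H the treatment effect is attenuated by the factor 1 − H × Var(U)/E(U), taken among those still at risk. The relative efficiency of the unadjusted test is the square of this factor averaged over events. The event fraction is 1374/9152 = 15.0%.

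Hand check at σ = 0.4: Var(U) = e^0.16 − 1 = 0.174. The average H over events is about −ln(0.85)/2 = 0.081. Then (1 − 0.081 × 0.174)² = 0.972, a loss of 2.8%. The full integration gives 2.7%.

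σ is an assumption throughout, because the protocol gives no prognostic strength. The c-index is approximated by Φ(σ/√2). Power at 1374 events comes from replacing D with 1374 divided by the relative efficiency.

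| σ (assumed) | c-index | Information lost, extended CV | Events for the same power if adjusted | Power at 1374 events if adjusted |
|---|---|---|---|---|
| 0.2 | 0.56 | 0.6% | 1365 | 90.2% |
| 0.3 | 0.58 | 1.5% | 1354 | 90.4% |
| 0.4 | 0.61 | 2.7% | 1337 | 90.8% |
| 0.5 | 0.64 | 4.2% | 1316 | 91.2% |
| 0.6 | 0.66 | 6.2% | 1288 | 91.8% |
| 0.7 | 0.69 | 8.7% | 1255 | 92.4% |

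With the CVD strata modelled explicitly (assumed prevalence 25% to 50%, CVD hazard ratio 2), the losses are 2.9% at σ = 0.4 and 9.3% at σ = 0.7.

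**3. Simulation checks.**
- 400 trials of 9152 patients, one covariate. At σ = 0.4 the mean |Z| is 3.174 unadjusted and 3.217 adjusted: (3.174/3.217)² = 0.973, a loss of 2.7%. At σ = 0.7 it is 3.015 and 3.162: 0.909, a loss of 9.1%.
- 900 trials of the 2×2 design with a stratified Cox test. For score variances 0.15, 0.30 and 0.50 (σ = 0.39, 0.55, 0.71), the ratios 3.341/3.387, 3.291/3.379 and 3.147/3.312, squared, give losses of 2.7%, 5.1% and 9.7%.

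**4. Core CV endpoint.** Its event fraction is not stated. At an assumed 8% to 10%, the loss is 1.4% to 1.8% at σ = 0.4 and 4.8% to 5.9% at σ = 0.7.

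**The case against.** **A stratified logrank is standard, valid and adequately powered, so this is a matter of preference.** The first part is right: the design reproduces, and nothing in the protocol is contradictory. But section 6.1.5.1 fixes the choice, the covariates are already collected, and adjustment keeps the type I error. It is a legitimate improvement of low priority.

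**Adjusted models are already planned.** Only in part. The exploratory models in section 6.1.5.1 contain both drugs and CVD history and may include age and sex. They omit lipids, and their results do not enter the closed procedure, so they add nothing to confirmatory power.

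**The size is not in the documents.** This stands. A reader might take a figure such as 3% to 11% as a property of this trial. The protocol gives no prognostic strength, and the loss is under 3% below σ = 0.4. A figure near 11% also comes from quoting the gain relative to the unadjusted test: (3.312/3.147)² − 1 = 10.8%, where the loss in the same scenario is 9.7%.

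**The risk score in section 6.2 could serve as the covariate.** A reader might infer this, but that section refers to early recruits only and names no components. It does not show that a score exists for all 9152 patients.

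**The slow event rate would be eased.** It would not. Sections 6.1 and 6.1.5.1 tie the final analysis to 1374 events, and adjustment leaves that unchanged.

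**The primary test would change after a formal interim analysis.** This is a real cost. It is limited because section 3.1.1.1 keeps the Executive/Steering Committee blinded and section 6.1.7 sets the final level by subtracting the alpha already spent, an argument that does not depend on which final statistic is used.

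**Conclusion.** The point holds as a modest efficiency gain. The four CV tests are valid, and the extended CV test reaches its stated 90% testwise power. They leave out age, sex and lipids, which are available on every patient before randomisation.

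If those covariates have a residual log-hazard SD of about 0.4 to 0.7 within CVD strata, the extended CV test loses about 3% to 9% of its information. At 1374 events that is worth roughly 1 to 2 power points. If the SD is 0.3, the loss is about 1.5% and the gain under half a point. The core endpoint loses less. The range rests wholly on the assumed SD. The effect within the closed procedure, where Table 7 gives 85.8% for the extended endpoint, would need its own simulation.

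The documents do not support reading this as an invalid or underpowered test, or as a way to shorten the trial. It is worth doing but not essential.

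**What to change.** In section 6.1.5.1, by amendment and before unblinding:

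- For N2, N3, V2 and V3, keep the stratified PHREG model and add a short fixed list: continuous age, sex, baseline lipids, and smoking if it is recorded for all patients.
- State the functional form of each covariate and a simple rule for missing baseline values.
- Name the statistic for the treatment term (for example its Wald test), because an overall score test of a model with covariates no longer isolates treatment.
- Use the resulting one-sided p-value in Table 6 at the level set in section 6.1.7.
- Keep the unadjusted stratified logrank as the supportive analysis.
- Do not build the covariate list on the section 6.2 risk score.

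The cost is amendment text and a few model terms, with no new data or patients. There are two small downsides. The hazard ratio becomes conditional on the covariates. The primary CV test is also changed after the December 2005 interim analysis, so the amendment should record that those choosing the covariates were blinded to treatment results. The 1374-event target and the trial's length do not change.
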